### 2.2 Secondary objectives

- To assess the safety and tolerability of intravitreal LFG316 Corporate Confidential Information in patients who meet the inclusion criteria. Corporate Confidential Information
- To assess the effect of intravitreal LFG316 Corporate Confidential Information on vitreous haze as measured on the Nussenblatt scale, ETDRS visual acuity, macular edema, presence or absence of chorioretinal lesions, and anterior chamber cells score in eyes with active NIU, in at least one eye, requiring intensification of systemic immunosuppressive therapy, and compared between Baseline and Days 2, 8, 15, 29, 43, 57, and 85. Corporate Confidential Information
- To evaluate the serum concentrations of total LFG316 and total CS during the course of the study.

The above objective applies to the study eye only.

# Corporate Confidential Information

However, patients can attend for unscheduled visits as needed and as determined by the investigator. Patients will be monitored for safety and ocular assessments obtained throughout treatment and follow-up periods. Patient eligibility will be assessed as outlined in [Figure 3-1](#) below.

## **Corporate Confidential Information**

## **Corporate ConfidentialInformation**

A summary of the study visits is shown in [Table 3-1](#) below.

**Table 3-1 Overall study scheme**

Corporate Confidential Information

	Screening Period	Treatment Period							
		1	2	3	4	5	6	7	8
Visit									
Day	-14 to -1	1	2	8	15	29	43	57	
LFG316 5 mg Intravitreal administration (n=16)		x				x		x	

## Corporate Confidential Information

### Corporate Confidential Information

During the screening period (Day -14 to Day -1), eligibility will be verified through applicable ophthalmic/medical history, ocular evaluations, vital signs, safety laboratory tests, electrocardiogram, and pregnancy test.

Ocular assessments include:

- Best corrected visual acuity (ETDRS)
- Intraocular pressure (IOP)
- Slit lamp biomicroscopy
- Dilated ophthalmoscopy
- Standardized vitreous haze score ([Nussenblatt et al 1985](#))
- Color fundus photos
- Spectral domain optical coherence tomography (sd-OCT): Study eye unless otherwise indicated.

- Anterior chamber cells
- Chorioretinal lesions (absent/present per investigator)
- Vasculitis (absent or present per Investigator)
- Presence of chorioretinal infiltrates due to uveitis
- Macular edema due to uveitis (absent or present per Investigator)

If either eye would qualify as the study eye, one eye will be selected as the study eye during the screening period based on the following criteria

- Higher vitreous haze score;
- If not determined by vitreous haze score, then by lower visual acuity;
- If not determined by visual acuity, investigator preference.

At Baseline, vital signs will be checked and compared to eligibility criteria.

Corporate Confidential Information

In preparation of the LFG316 IVT injection, personnel from the study clinic should follow the LFG316 preparation and instruction manuals. These are provided separately. Patients randomized to LFG316, will receive a single IVT dose of LFG316. Postdose safety assessments and ocular examination will occur after the IVT injection. PK/PD blood collection will occur prior to dosing.

Corporate Confidential Information

Patients will return for scheduled follow-up visits (see [Section 3.1](#)), where ocular exams and safety assessments will take place. Safety laboratory studies and ECG will be done at the specified times throughout the trial and at the end-of-study visit.

For assessment details, refer to the [Assessment schedule](#).

### **3.2 Rationale of study design**

This is a randomized, prospective, proof-of-concept study of intravitreal LFG316 in patients with active NIU who require intensification of systemic immunosuppressive therapy to manage their disease.

This population has been selected as they may benefit from local anti-CS therapy such as LFG316 and reflect a future patient population for which this compound may be developed. Eligible patients who present with a flare and who are on systemic corticosteroids or non-steroid immunosuppressants will have their therapy tapered or stopped, respectively, at the time of intravitreal LFG316 administration. This discontinuation of systemic immunosuppressive therapy will allow for a true assessment of local LFG316 activity in

controlling the inflammation associated with NIU. Patients who do not respond to IVT therapy can be rescued by the investigator at any time and must be discontinued per protocol if their condition worsens or if they lose vision. Corporate Confidential Information

Patients will be monitored for safety and ocular assessments obtained throughout treatment and follow-up periods.

Corporate Confidential Information

Women of child-bearing potential (WOCBP) will be included because women are equally affected by NIU and the disease is most prevalent in patients aged 20 to 50 years, however they need to have effective contraception as explained on [Section 4.1](#).

### **3.3 Rationale of dose/regimen, duration of treatment**

Corporate Confidential Information

The treatment duration of 85 days was chosen as the period beyond which lack of response would be confidently interpreted as lack of efficacy; it is based on clinician estimates of the time course of NIU response to conventional therapies. Assessing the primary endpoint at Day 85 allows assessment of treatment effect after the patients have received the full benefit of a course of LFG316 (3 doses).

The treatment interval is based on comparison to the pharmacodynamics of other intravitreal monoclonal antibodies such as ranibizumab and bevacizumab. Similar to other intravitreal medications, the appropriate dose and interval will be determined empirically in Phase II/III.

Corporate Confidential Information

## Corporate Confidential Information

### **3.4 Rationale for choice of comparator**

Not applicable.

### **3.5 Risk/ Benefit for this study**

Should int:ravitreal LFG316 be effective in NIU, patients may experience reduced intraocular inflammation and improved vision.

To date, LFG316 has been administered to 153 patients via IVT injection, 90 of whom have received monthly ea.,,,,LFG316 injections (See [Section 1.1.1.6](#)) for up to 18 months with good safety and tolerability. This includes the administration of over 2000 IVT injections. No dmg related toxicity was observed in trials with LFG316 at single doses of up to " " and with repeat dosing of intravitreal L FG3 1 6 at c.,..c-o.

IVT administration of LFG316 has been shown to result in relatively low levels of serum antibody concentration and no measurable suppression of serum complement activity (as measured by the Wieslab assay)      **Corporate Confidential Information**

Thus, no systemic complement suppression is suspected in the present study with IVT administration.

However, local immunosuppression could in the01y increase the eye ' s susceptibility to infection, including endophthalmitis. Across all ongoing clinical trials with LFG316, the incidence of endophthalmitis (0.09%) has been similar to the background rate of 0.03% to 0.13% per injection in the general population. With respect to endophthalmitis, the protocol uses cmTent best practices to reduce endophthalmitis rates.

The reportedAEs and SAEs, including deaths, (See [Section 1.1.1.6](#)) are in agreement with those expected for the various patient populations and IVT procedures employed in the administration of LFG316. Per the Reference Safety information (See investigator brochure) the expected adverse events considered 'Very Common' include conjunctival haemorrhage, vitreous floaters, vitreous detachment, and increased lacrimation. Events considered 'Common' include Endophthalmitis and Increased intraocular pressure. The assignment of 'common' for endophthalmitis is based on 2 cases of endophthalmitis observed in 153 patients. Both cases

were due to a common skin pathogen (*staph. Epidennidis*). Overall, these events are most likely associated with the injection procedure and not a specific chug-related toxicity. To monitor patients for these and other unexpected adverse events a comprehensive panel of ocular safety assessments based on the Phase I and Phase II studies with LFG31 6 as well as that for other of intravitreal medications will be conducted on all patients emolled. The study also includes systemic safety assessments (serum chemistries, hematology, and electrocardiogram) at Screening and end-of-study to fmther profile any systemic changes that could be associated with the patient's disease or trntment with LFG316.

All IVT injections cany a risk of endophthalmitis, retinal detachment, vitreous or retinal hemonhage, cataract, elevated intraocular pressure, and ocular inflammation. LFG316 itself could cause, in theo1y, adverse effects such as increased risk of endophthalmitis, cataract, elevated intraocular pressure, ocular inflanunation, and retinal toxicity. Patients with NIU are at inherent risk for some of these complications. LFG316 could cause existing NIU to worsen. Each of the above outcomes would be apparent on eye exam, and most would cause symptoms that would prompt the patient to seek evaluation.

As with any antibody, LFG3 1 6 may cany the risk of hypersensitiivty and patients should be monitored and managed per local center practice. LFG316 may elicit immunogenicity and the fonnation of anti-LFG316 antibodies; this has not been detected in any LFG316 trials to date.

Regarding women of childbearing potential (WOCBP): to participate in this study, these patients must use effective contraception. Treatment of NIU often requires systemic immunosuppressive therapy with medications in Pregnancy Categories D and X (e.g., mycophenolic acid). By comparison for C5 inhibition with LFG316: inborn deficiency of CS target in mice, inborn deficiency in human offspring, and haploinsufficiency in human mothers and fathers have not been associated with reproductive or embryofetal toxicity ([Rosenfeldet al 1976](#); [Haeney et al 1980](#); [Cesbron et al 1985](#); [Sanal et al 1992](#); [Delgado-Celviiio et al 2005](#); [Lopez-Lera et al 2009](#); [Zerzri et al 2010](#)). Case se1es on the use of another anti-CS monoclonal antibody, eculizumab, during any or all trimesters of pregnancy have not identified any bi1th defects ([Danilov et al 2010](#)). For reasons mentioned above, no systemic effect on the complement cascade is expected.

Overall, patients with NIU are expected to derive a benefit from participating in this trial with LFG31 6. In the event activity of LFG31 6 is not sufficient to control the inflammatol1y disease in this patient population, rescue therapy will be implemented per protocol or at the discretion of the investigator to minimize the risk to patient's vision.

### **3.6 Purpose and timing of interim analyses/design adaptations**

Corporate Confidential Information

## 4 Population

The investigator must ensure that all subjects being considered for the study meet the following eligibility criteria. No additional exclusions should be applied by the investigator, in order that the study population will be representative of all eligible subjects.

Subject selection is to be established by checking through all inclusion/exclusion criteria at screening and study baseline. A relevant record (e.g., checklist) must be stored with the source documentation at the study site.

Replacement subjects will be emolled to replace subjects who discontinue the study for reasons other than safety, e.g., use of systemic immunosuppressive therapy to rescue fellow eye.

Deviation from **any** entry criterion excludes a subject from emollement into the study. It is expected that approximately 24 patients with NIU requiring intensification of systemic immunosuppressive therapy will be emolled in the study.

### 4.1 Inclusion criteria

Patients eligible for inclusion in this study must fulfill **all** of the following criteria:

1. Written informed consent must be obtained before any assessment is performed.
2. Male or female patients 18 years or older.
3. Active NIU, in at least one eye, as defined below, in patients requiring intensification of systemic immunosuppressive therapy:
  - Vitreous haze of at least 1+ at screening on the scale of [Nussenblatt et al 1985](#), or
  - Chorioretinal lesions due to uveitis (chorioretinal lesions due to infectious uveitis are excluded)
  - Patients who present with a flare and who are at the time of the emollement on systemic corticosteroid or non-steroidal immunosuppressants will have their therapy tapered or stopped, respectively, at the time of intravitreal LFG316 administration.
4. ETDRS visual acuity of 20 letters (20/400) or better in the study eye.
5. Women of child-bearing potential (WOCBP), defined as all women physiologically capable of becoming pregnant, unless they are using effective methods of contraception during dosing of study treatment and 7 weeks (5 times the terminal half-life) of LFG316.

***Effective contraception methods include:***

- Total abstinence (when this is in line with the preferred and usual lifestyle of the subject). Periodic abstinence (e.g., calendar, ovulation, symptothermal, post-ovulation methods) and withdrawal are not acceptable methods of contraception
- Female sterilization (have had surgical bilateral oophorectomy with or without hysterectomy), total hysterectomy or tubal ligation at least six weeks before taking study treatment. In case of oophorectomy alone, only when the reproductive status of the woman has been confirmed by follow up hormone level assessment
- Male sterilization (at least 6 months prior to screening). For female subjects on the study, the vasectomized male partner should be the sole partner for that subject

- Barrier methods of contraception: Condom or Occlusive cap (diaphragm or cervical/vault caps). For UK: with spermicidal foam/gel/film/cream/ vaginal suppository
  - Use of oral, injected or implanted hormonal methods of contraception or other forms of hormonal contraception that have comparable efficacy (failure rate <1%) for example hormone vaginal ring or transdermal hormonal contraception
  - Placement of an intrauterine device (IUD) or intrauterine system (IDS)
  - In case of use of oral contraception women should have been stable on the same pill for a minimum of 3 months before taking study treatment.
6. Able to communicate well with the investigator, to understand and comply with the requirements of the study.

## 4.2 Exclusion criteria

Patients fulfilling **any** of the following criteria are not eligible for inclusion in this study:

Clinically significant abnormality in screening laboratory results or electrocardiogram (see below for definition on the term "clinically significant").

1. Uveitis that is so severe that, in the investigator's judgment, it is too likely to test an experimental drug.
2. Bilateral uveitis for which, in the opinion of the investigator, systemic immunosuppressive therapy is required to manage the inflammation in the fellow eye; **use of local therapy in the fellow eye is acceptable and not an explicit exclusion** (See [Section 5.5.7](#) for acceptable concomitant treatments).
3. History of retinal detachment
4. In the study eye, cataract expected to interfere with study conduct or require surgery during the study.
5. Pregnant or nursing (lactating) women, where pregnancy is defined as the state of a female after conception and until the termination of gestation, confirmed by a positive hCG laboratory test (>5 mIU/ml).
6. History of hypersensitivity to any monoclonal antibody (mAb).
7. History of infectious uveitis or endophthalmitis in either eye
8. Anticipated need for intraocular surgery during the study period
9. Participation in another interventional clinical study within 12 weeks prior to the start of study treatment.
10. Any medical, psychiatric, or substance-use condition likely to interfere with the patient's participation in the study, or likely to cause serious adverse events during the study.
11. Uveitis with an underlying diagnosis that is uncertain and which would reasonably include a disease for which immunosuppression would be contraindicated (e.g., when the diagnosis of ocular lymphoma, histoplasmosis, toxoplasmosis, etc., are a reasonable possibility) or for which immunosuppression is not proven to be beneficial (e.g., acute zonal occult outer retinopathy, progressive outer retinal necrosis, acute retinal necrosis syndrome, etc.).
12. Forms of uveitis that may spontaneously resolve such as multiple evanescent white dot syndrome (MEWDS).

13. Current use of or likely need for systemic medications known to be toxic to the lens, retina, or optic nerve (e.g., deferoxamine, chloroquine, ethambutol, etc.).
14. Change in low-molecular-weight immunosuppressive medications during the 3 weeks prior to baseline; this does not apply to corticosteroid doses.
15. Patient is taking corticosteroids or another systemic immunosuppressive medication for any extraocular disease or concurrent medical condition **unrelated** to uveitis (e.g., multiple sclerosis, organ transplantation, moderate or severe asthma, autoimmune disease, etc.) and the tapering or discontinuation of the immunosuppression, including corticosteroids would not be safe because of the risk of exacerbation of the extraocular condition; the patient would be excluded.
16. Any systemic immunosuppressive biologic agent given via intravitreal, intravenous or subcutaneous route such as:
  - Infliximab, daclizumab, etanercept, adalimumab, etc. **within 4** months prior to Day 1
  - Depleting antibodies, e.g., rituximab and alemtuzumab, are excluded for **12 months** prior to Day 1
17. Periocular or intra-vitreal drugs (e.g., corticosteroids) administered to the study eye within three months prior to Day 1.
18. Presence of ocular opacities that, in the opinion of the investigator, preclude imaging and/or reasonable vitreous haze scoring
19. Chronic hypotony (IOP < 6 mmHg) in either eye
20. Ozurdex® (dexamethasone intra-vitreal implant) administered in the study eye during the 6 months prior to Day 1
21. Retisert® (fluocinolone acetonide intravitreal implant) administered to the study eye within the 3 years prior to Day 1.
22. Topical ocular steroid therapy greater than the equivalent of prednisolone acetate 1% every hour while awake within 1 week of Day 1.
23. Uncontrolled glaucoma or ocular hypertension in either eye, defined as an intraocular pressure (IOP) > 30 mmHg while on relevant therapy
24. Ocular surgery in the study eye within the last 4 months except for a diagnostic vitreous or aqueous tap with a small-gauge needle.
25. Laser photocoagulation in the study eye within 3 months prior to Day 1.

No additional exclusions may be applied by the investigator, in order to ensure that the study population will be representative of all eligible patients.

#### **4.2.1 Interpretation of laboratory and electrocardiogram results**

Any of the following results in isolation need not be considered clinically significant: low **or** moderately elevated serum cholesterol or triglycerides; moderately low serum creatinine; moderately elevated serum glucose in a patient known to have diabetes mellitus; or urine white cells or positive leukocyte esterase in an patient without genitourinary symptoms. In the setting of a normal white blood count, mild anomalies in the leukocyte differential will not be considered clinically significant. On electrocardiogram, stable sinus bradycardia will not be considered clinically significant.

## 5 Treatment

## 5.1 Investigational treatment

The LFG3 16 solution for inject ion is a liquid solution at a concentration of Capon, °\*\*\*\*\*-  
The vials contam CarpanCoA. of active ingredient which conesponds to a volume of  
The LFG316 solution for injection is also be manufactured and packaged by Novaltis and  
supplied to the investigator in bulk in an open label fashion. Both f01mulations are cons idered  
equivalent.

Medications used as a part for IVT injection procedure need to be recorded in the appropriate concurrent medication eCRF page.

### 5.1.1 Bio-batch Retention samples

Not applicable.

## 5.2 Treatment arms

Study patients will be randomized in 2:1 ratio to receive;

- LFG31 6 (n=16) administered intravitreally or

## 5.3 Treatment assignment

All study patients will be randomized to either receive c.,...,~ of LFG316 administered intravitreally or ~~coipora~~ Confidential Information according to treatment assignment. The ~~random~~ numbers will be generated using the following procedure to ensure that treatment assignment is unbiased and concealed from masked evaluator(s). A randomization list will be produced by, or under the responsibility of Novartis Drug Supply Management using a validated system that automates the random assignment of treatment aims to randomization numbers in the specified ratio. The randomization scheme for patients will be reviewed and approved by a member of the randomization office.

## 5.4 Treatment masking

The investigator, patients, and Novartis will not be masked to treatment condition. An evaluator at each site will be masked to treatment condition. The patient will be instructed not to divulge his or her treatment assignment to this evaluator.

## 5.5 Treating the patient

### 5.5.1 Patient numbering

## Screening number

Each patient screened is assigned a unique screening number. The screening number is a combination of the center number that is provided by Novalis and a three digit number starting with 001 for each subject which is assigned by the Investigator. Therefore, if the center number is 1 (any leading 0's in the center number are dropped) the screening numbers

will be assigned such as 1001, 1002, 1003, etc. in ascending order. If the center number is 2 (or 0002), the screening numbers will be 2001, 2002, 2003, etc. in an ascending order.

### **Treatment number**

If the patient is deemed eligible for enrollment into the study and will commence the dosing period, site study personnel will contact Novartis clinical trial leader or designee and a treatment number will be assigned for this patient.

Once assigned to a patient, a treatment number will not be reused.

There should be a source document maintained at the site which links the screening number to the treatment assignment number (once assigned).

Treatment numbers will be assigned in ascending, sequential order to eligible patients in accordance with entry into the study. The treatment number becomes the definitive patient number as soon as a patient receives the first dose of the respective study treatment.

The investigator will enter the treatment number on the eCRF.

Patients will be assigned a treatment number beginning with 5001 up to 5072. If a patient discontinues prior to completing the trial, they may be replaced. The replacement patient will be assigned a randomization number corresponding to the original patient number and treatment (e.g., we will replace patient 5003 with 6003).

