### 5.5.6.2    **Rescue of fellow eye**

The investigator will care for the fellow eye at his or her discretion. There are no restrictions on topical, periocular, or intravitreal therapy in the fellow eye other than those noted in [Section 5.5.7; Table 5-1](#).

NOTE: If during the trial, a patient requires systemic immunosuppressive therapy for the fellow eye, investigational therapy for the study eye should be stopped and conventional therapy instituted. The patient should continue in the study for assessment purposes. Patients who require systemic immunosuppressive therapy may be replaced to maintain adequate study power if the treatment was implemented for the sole purpose of treating the fellow eye.

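### In this open-label trial a replacement patient takes the known arm of the patient replaced, so replacements are not randomised and selection bias has a way in

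*Protocol*

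**What the plan says.** **Allocation of replacements.** Protocol Section 5.5.1 (Treatment number) provides that "The replacement patient will be assigned a randomization number corresponding to the original patient number and treatment". Its example replaces patient 5003 with 6003. Ordinary numbers are covered by "Patients will be assigned a treatment number beginning with 5001 up to 5072", issued in ascending order as patients enter.

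**Who issues the number.** Once a patient is judged eligible, "site study personnel will contact Novartis clinical trial leader or designee and a treatment number will be assigned for this patient".

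**Masking.** Section 5.4: "The investigator, patients, and Novartis will not be masked to treatment condition". Only an evaluator at each site is masked.

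**Randomisation.** Section 5.3 says all study patients are randomised from a list produced under the sponsor's drug supply group, with a procedure meant "to ensure that treatment assignment is unbiased". The concealment it promises is from the masked evaluators; it does not mention the people who enrol patients.

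**When replacement applies.** Three places differ:
- Section 5.5.1: "If a patient discontinues prior to completing the trial, they may be replaced".
- Section 4: replacements will be enrolled "to replace subjects who discontinue the study for reasons other than safety, e.g., use of systemic immunosuppressive therapy to rescue fellow eye".
- Section 5.5.6.2: patients who need systemic immunosuppression "may be replaced to maintain adequate study power if the treatment was implemented for the sole purpose of treating the fellow eye".

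**The concern.** Copying the arm of the patient replaced does little harm in a blinded trial, because nobody who recruits knows what that arm is. Here it is known. When 5003 leaves, the treatment attached to 6003 is fixed and visible to unmasked people before anyone is chosen to fill the slot.

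Two things follow. First, the replacement's arm does not come from a random draw made for that patient, so Section 5.3 is not true of replacements. Second, whoever decides which patient becomes the replacement could, deliberately or not, let prognosis influence who enters a known arm. A masked evaluator protects the assessment of the outcome but does nothing about who is assigned to which arm.

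The result most exposed is the 90% confidence interval for the difference in response rates (Protocol Section 9.4.1), because only randomisation makes the arms comparable. The LFG316 response rate set against 60% (synopsis, sample size; SAP Section 7.1) can also move if better-prognosis patients fill LFG316 slots.

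**Working it through.** **1. Is the arm of a replacement known in advance?**
- The 60xx number carries the treatment of the matching 50xx patient (5.5.1).
- The sponsor, the investigator and the patient know that treatment (5.4).
- The sponsor's trial leader or designee issues the number (5.5.1).

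The sponsor therefore has foreknowledge in every case, and the original site has it whenever it recruits the replacement. For another site, the documents do not say whether it is told in advance.

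**2. Does the sequential-order sentence settle which number comes next?** No. Read literally, 6003 comes after 5072, so with about 24 patients planned a replacement number would never be reached. Section 5.5.1 gives no other rule for choosing between a waiting 60xx number and the next 50xx number, and does not say whether the replacement must come from the same site.

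**3. Share of patients affected.** The number of replacements *k* is not in the documents; 2 to 4 is an assumption. With 24 planned patients, the share is k/(24 + k):

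| k | share of all enrolled |
|---|---|
| 2 | 2/26 = 7.7% |
| 3 | 3/27 = 11.1% |
| 4 | 4/28 = 14.3% |

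**4. The plan's own operating characteristics.** Inputs from the synopsis: n = 16, null rate 0.60. The upper tail is P(X ≥ r) = Σ C(16, x) pˣ(1 − p)¹⁶⁻ˣ for x = r to 16.

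| r | p = 0.60 | 0.70 | 0.80 | 0.85 |
|---|---|---|---|---|
| 12 | 0.1666 | 0.4499 | 0.7982 | 0.9209 |
| 11 | 0.3288 | 0.6598 | 0.9183 | 0.9765 |

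The stated 17% and 45%, 80%, 92% are reproduced by 12 or more responders, not by 11 or more. Step 6 therefore uses 12 or more.

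**5. Illustrative shift in the estimates.** Suppose k of the 16 LFG316 patients are selected replacements who would respond at rate q without any drug benefit, and the others at 0.60. The expected LFG316 rate moves by (k/16) × (q − 0.60):
- k = 1, q = 0.70: 1/16 × 0.10 = 0.6 points
- k = 2, q = 0.80: 2/16 × 0.20 = 2.5 points
- k = 4, q = 0.90: 4/16 × 0.30 = 7.5 points

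If the other arm is unaffected, the difference between arms moves by the same amount. The other arm has 24 − 16 = 8 patients, so each selected patient there carries twice the weight (1/8 against 1/16).

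**6. Illustrative effect on the 60% comparison.** Same set-up, exact probability of 12 or more responders when the drug adds nothing:

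| k | q = 0.70 | q = 0.80 | q = 0.90 |
|---|---|---|---|
| 0 | 0.167 | 0.167 | 0.167 |
| 1 | 0.179 | 0.192 | 0.205 |
| 2 | 0.193 | 0.220 | 0.249 |
| 4 | 0.222 | 0.285 | 0.357 |

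Both k and q are assumed throughout steps 5 and 6. The figures show what selection of that strength would do, not how much is expected.

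**The case against.** The other side has several fair points.

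- **The site calls only after eligibility is established.** A reader might infer that every site knows the arm before it screens a candidate. The documents do not support that. Foreknowledge is shown for the sponsor, and for the original site if it recruits the replacement.
- **Section 4 says replacements will be enrolled.** A reader might infer that replacement is mandatory and so frequent. Sections 5.5.1 and 5.5.6.2 make it optional, and 5.5.6.2 limits it to treatment given for the fellow eye alone. Rescued patients are asked to keep attending visits (Sections 5.5.6 and 6), so rescue is not automatically a discontinuation. No frequency can be inferred.
- **The main test is single-arm.** It compares LFG316 with a fixed 60% and does not rest on randomisation. The SAP adds that no decision should be based on its p-value. It would therefore be wrong to say that one steered patient could decide the trial at the boundary between 11 and 12 responders. The estimates and intervals will still be reported, and selection can bias them.
- **Investigators may not add exclusions** (Sections 4 and 4.2). This limits steering but does not remove it: exclusions 1 and 2 rest on the investigator's judgement about severity and about the fellow eye.
- **Same-arm replacement keeps the LFG316 arm at 16.** This is a real purpose. With independent 2:1 draws, each lost LFG316 patient has a 1/3 chance of being replaced in the other arm. If 2, 3 or 4 leave, the chance that not all are restored is 1 − (2/3)ᵏ = 56%, 70% or 80%. That is a genuine cost, but usually a small shortfall: the expected number not restored is k/3, or 0.7 to 1.3 patients.

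**Conclusion.** The point holds. Replacement patients are allocated by a rule whose result unmasked people already know, contrary to Section 5.3, and the order in which 60xx and 50xx numbers are used is not settled. This rests on the protocol's text alone.

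The size is conditional. Under the assumed 2 to 4 replacements, 8% to 14% of enrolled patients would not be randomised. Any resulting bias depends also on how strongly prognosis influenced selection, on which the documents give no information. The between-arm 90% interval is the main casualty and the comparison with 60% a secondary one. The documents open a route for selection bias; they do not show that selection would occur. The change is worth making because it is cheap and closes that route.

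**What to change.** 1. In Section 5.5.1, delete the same-treatment rule and the 5003/6003 example. Insert: *A replacement patient receives the next unused number on the concealed randomisation list. The number is released only after eligibility has been confirmed and recorded.*
2. Confirm that the list covers enough entries beyond the first 24. The range 5001 to 5072 leaves 72 − 24 = 48 numbers, but it is a treatment-number range, and no section says the randomisation list has 72 entries.
3. Reconcile the conditions for replacement in Sections 4, 5.5.1 and 5.5.6.2 so that one statement applies.
4. Report the exact binomial operating characteristics at the LFG316 sample size achieved.

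The cost is one rewritten paragraph, one reconciled condition and an instruction to the person who releases numbers. The final split may differ from 16:8 by a patient or two, and the LFG316 arm may not return to exactly 16; item 4 deals with that. No dose, schedule or clinical rule changes.
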